1.6.3. Genotoxicity

Negative results were obtained in bacterial reverse mutation assays.³⁰

In vitro chromosomal aberration tests performed in a cell line derived from Chinese hamster lung (CHL/IU cells) showed that FF-10501-01 induced chromosomal aberrations both with and without metabolic activation.³¹

1.6.4. Phototoxicity

The findings of visible-ultraviolet absorption spectrometry of FF-10501-01 indicate a low potential for phototoxicity.³²

Additional information can be found in the FF-10501-01 Investigator's Brochure.

1.7. FF-10501-01 Experience in Humans

1.7.1. Japan Phase 1 Study

A Phase 1 study of FF-10501-01 conducted by FUJIFILM (Toyama Chemical) in Japan in patients with MDS, was completed. In this study, patients received FF-10501-01 at doses of 200, 300 and 400 mg BID (400, 600 and 800 mg/day) for 14 days continuously followed by 14 days off therapy (28-day cycle).³³ A total of 9 patients were treated. No DLTs were observed. One study drug-related serious adverse event (SAE) (Grade 4 neutropenia) occurred in Cycle 1 in one subject treated with FF-10501 800 mg/day. Two study drug-related SAEs (Grade 3 anemia and Grade 3 pneumonia) occurred in Cycle 5 in two subjects treated with FF-10501 400 mg/day. The most common adverse events (AEs) in all patients, regardless of causality, were anemia, rash, and platelet count decreased (33.3%, 3 of 9

subjects each). The treatments after cycle 1 were extended in 8 patients out of 9 in each treatment cohort; 3 at 400 mg/day, 3 at 600 mg/day and 2 at 800 mg/day.

The median number of treatment cycles were 4 (range 2-5) at 400 mg/day, 13 (range 2-18) at 600 mg/day, and 2 (range 1-7) at 800 mg/day. One patient at 600 mg/day has received a total of 18 cycles to date and remains on study. C_{max} and AUC increased with increasing FF-10501-01 dose. T_{max} was 2 to 4 hours and the drug was nearly eliminated within 24 hours after administration. The cumulative urinary excretion rate of FF-10501 up to 24 hours after administration was 25 to 45%. No accumulation of FF-10501 was observed.

1.7.2. U.S. Phase 1/2a Study

Study FF1050101US101 is ongoing in the United States in patients with AML, MDS or CMML. In Phase 1, dose levels of 50, 100, 200, 300, 400 and 500 mg/m² BID for 14 days, followed by 14 days off therapy, or 400 mg/m² BID for 21 days, followed by 7 days off therapy, repeated every 28 days have been studied to date. A total of 33 patients have been treated to date on study (25 AML, 8 MDS).

Three events of drug-related atrial fibrillation (Grade 2) were reported in 2 subjects at a dose of 500 mg/m² BID (Cohort 6). Study drug was suspended in both subjects and all events resolved with oral metoprolol treatment. These events were medically important events and thus met the definition of dose-limiting toxicity (DLT). No further enrollment was made at this dose level. The maximally tolerated dose (MTD) was declared at 1 dose level below the dose eliciting DLT, 400 mg/m² BID, and this cohort was expanded to 6 subjects. No DLTs have been observed in N=7 total subjects treated at 400 mg/m² BID x 14 days.

At the MTD of 400 mg/m² BID, Cohort 7 was added to extend the BID dosing schedule to 21 days followed by 7 days off, repeated every 28 days (=1 cycle) (Amendment 3). No DLTs occurred have occurred to date.

At the MTD of 400 mg/m² BID, Cohort 8 was added to extend the BID dosing schedule to 28 days continuous dosing (=1 cycle) (Amendment 4). No DLTs have occurred to date.

The median number of prior treatments is 2 (range 1 - 7), all relapsed or refractory to prior hypomethylating agents (azacitidine, decitabine). The median number of treatment cycles is 2 (range 1 – 28).

The most common AEs include Grade 1 or 2 fatigue, diarrhea, and nausea, with drug-related Grade 3 or 4 AEs reported for 1 patient in the 200 mg/m² BID dose group (thrombocytopenia, neutropenia and bone marrow aplasia) and 1 patient in the 300 mg/m² BID dose group (mucositis); the events resolved without sequelae.

Partial remissions have occurred in 3 AML patients (50, 100 and 400 mg/m² BID) after 1 – 3 cycles, lasting for at least 28, 5 and 6 cycles, respectively. A total of 8/25 (32%) AML patients, including the 3 PRs, have attained stable disease control with no disease progression over 4 – 28 cycles. A marrow complete response was achieved in 1 MDS patient treated at 400 mg/m² BID x 14 days after 1 cycle and was sustained for 14 cycles. A major platelet response was observed in 1 patient treated at 400 mg/m² BID x 21 days, sustained for 1 cycle. Four of 8 MDS patients (50%), including the marrow CR, attained stable disease control with no disease progression over 3, 5, 14 and 17 cycles, respectively.

FF-10501-01 was rapidly absorbed with mean T_{max} of 2.74 hours and mean $t_{1/2}$ of 4.05 hours. Drug exposure (AUC_{0-24} and AUC_{course}) increased with dose in a near linear manner.

Potent suppression of circulating xanthosine monophosphate (XMP), a marker of IMPDH activity, has been observed following FF-10501-01 administration on Day 1 of Cycles 1 and 2 at doses $\geq 50 \text{ mg/m}^2 \text{ BID}$.

1.8. Dose Rationale

In the SM-108 Phase 2 study described above, patients with hematologic malignancies showed responses at oral doses of 200 – 300 $\text{mg/m}^2 \text{ BID}$ (400 – 600 $\text{mg/m}^2/\text{day}$) administered for 14-day cycles. The toxicology findings in repeat dose studies in the rat and dog indicate a dose of 15 mg/kg (equivalent to 90 mg/m^2) in the rat for up to 1 month was well-tolerated with few effects, and a dose of 10 mg/kg (equivalent to 200 mg/m^2) in the dog up to 1 month exhibited no adverse effects. The dog appears to be the more relevant toxicology species based on prior human safety experience. Therefore, the starting dose in this study will be 50 $\text{mg/m}^2 \text{ BID}$, which represents a 4-fold margin of safety over the MTD in the dog, escalating to 500 $\text{mg/m}^2 \text{ BID}$, administered orally in 14-day cycles.

Since the study started, FF-10501-01 has been found to be well-tolerated up to a dose of 400 $\text{mg/m}^2 \text{ BID}$ orally x 28 days continuous dosing. Long-term stable disease has been observed in some MDS and AML patients (up to 28 cycles), as noted above.

The regimen for phase 2 is 400 $\text{mg/m}^2 \text{ BID}$ x 21 days out of a 28-day cycle.

2. STUDY OBJECTIVES

2.1. Primary Objective:

- To determine the safety and tolerability in subjects who receive FF-10501-01 for the treatment of advanced hematologic malignancies

2.2. Secondary Objective:

- To determine the overall response rates
- To evaluate the proportion of subjects who achieve hematologic improvement in peripheral blood or bone marrow blast count
- To evaluate progression-free survival (PFS)
- To evaluate overall survival (OS)
- To evaluate the pharmacokinetics of FF-10501 and M1
- To evaluate the xanthosine monophosphate (XMP) as a pharmacodynamic marker

3. INVESTIGATIONAL PLAN

3.1. Overall Study Design

This is a Phase 1/2a, dose-escalation study of FF-10501-01 for the treatment of advanced hematologic malignancies.

A total of up to N=68 subjects will be enrolled in the study. Subjects with acute myelogenous leukemia (AML) (Phase 1 only), myelodysplastic syndrome (MDS), and chronic myelomonocytic leukemia (CMML) will be included.

Major selection criteria are: age \geq 18 years, confirmed MDS/CMML or AML (Phase 1 only for AML) with documented disease progression following previous therapy, or subjects with AML \geq 60 years of age who are not candidates for other therapies (Phase 1 only). Subjects must be \geq 3 weeks beyond chemotherapy, radiotherapy, major surgery, or other experimental treatments, and recovered from all acute toxicities (\leq Grade 1), have adequate renal and hepatic function, and no known history of significant cardiac disease.

Phase 1:

14-day Schedule: Following Screening, a total of 6 cohorts of 3 subjects each received oral doses of 50, 100, 200, 300, 400 or 500 mg/m² BID per day (100, 200, 400, 600, 800 or 1000 mg/m²/day) for 14 days, followed by 14 days off, repeated every 28 days (= 1 cycle). Three events of drug-related atrial fibrillation (Grade 2) were reported in 2 subjects at a dose of 500 mg/m² BID (Cohort 6). Study drug was suspended in both subjects and all events resolved with oral metoprolol treatment. These events were medically important events and thus met the definition of dose-limiting toxicity (DLT). No further enrollment was made at this dose level. The maximally tolerated dose (MTD) was declared at 1 dose level below the dose eliciting DLT, 400 mg/m² BID, and this cohort was expanded to 6 subjects. No DLTs have been observed in N=7 total subjects treated at 400 mg/m² BID x 14 days.

21-day Schedule: At the MTD of 400 mg/m² BID, Cohort 7 was added to extend the BID dosing schedule to 21 days followed by 7 days off, repeated every 28 days (=1 cycle) (Amendment 3).

28-day Schedule: At the MTD of 400 mg/m² BID, Cohort 8 was added to extend the BID dosing schedule to 28 days continuous dosing each 28 days (= 1 cycle) (Amendment 4).

DLT is defined as Grade 4 hematologic toxicity lasting 7 days or more; Grade 3 nonhematologic toxicity of any duration not amenable to supportive care; failure of platelets, absolute neutrophil count (ANC), or hemoglobin (Hb) to recover to Grade 1 within 12 weeks despite use of platelet and red blood cell (RBC) transfusions and/or growth factors; febrile neutropenia (defined as ANC<1000/mm³ with a single temperature of $>38.3^{\circ}\text{C}$ or sustained temperature of $\geq 38^{\circ}\text{C}$ for over one hour); Grade 3 thrombocytopenia associated with bleeding; or other important medical event.

For all subject cohorts, if 1 of 3 subjects per cohort experiences DLT, the cohort will be expanded to 6. If 2 of 6 subjects per cohort experience DLT, all further dose escalation will stop. If 0 of 3 or \leq 1 of 6 subjects per cohort experience DLT by Day 28 following dosing of FF-10501-01, dose escalation will proceed to the next cohort. At the MTD of 400 mg/m² BID, the longest schedule of administration below the schedule of administration eliciting

DLT will be declared the recommended Phase 2 dose (RP2D) and schedule. A total of 6 subjects will be treated at the RP2D and schedule. No intra-subject dose escalation will be allowed from previous dose levels/schedules of administration until at least one subject has completed Cycle 1 at the longer schedule of administration (e.g., 21 or 28 days) with no Grade 2 or greater toxicities observed.

Additionally, patients currently on study will have the option to extend their current dosing schedule to 21 days, followed by 7 days off, repeated every 28 days (=1 cycle) or 28 days of continuous dosing, whichever is chosen as the best schedule, if seen in the patient's best interest by the principal investigator. Dose level adjustments for DLT will be made. Subjects who experience DLT at the first dose level, 50 mg/m² BID, will not be dose-reduced. Up to 48 subjects are planned for Phase 1.

Phase 2a: Once 6 subjects are treated at the RP2D and schedule in Phase 1, 1 additional cohort will enroll 20 subjects with MDS/CMML who have relapsed from, or are refractory to, prior hypomethylating agent (HMA) therapy. Subjects enrolled in Phase 1 at the RP2D and schedule and who meet the Phase 2a selection criteria will count towards the Phase 2a accrual. Dose level adjustments for adverse events will be made.

During the study, a Safety Review Committee, consisting of the actively recruiting investigators, the Medical Monitor, and FPHU, will review data from each cohort on an ongoing basis.

Subjects on the 21-day schedule will receive FF-10501-01 on a BID schedule. For all subjects on the 21-day dosing schedules, blood samples for pharmacokinetic assessment of FF-10501 and M1 in plasma will be collected on Cycle 1 Day 1 pre-dose (any time), between 0.5-1 hr post-dose, and between 2-4 hr post-dose, and Day 15 pre-dose (within 15 minutes prior to dosing), between 0.5-1 hr post-dose, and between 2-4 hr post-dose.

Blood concentration of xanthosine monophosphate (XMP) will be assessed as a pharmacodynamic endpoint.

For subjects on the 21-day dosing schedules, blood samples for XMP assessment will be collected on Cycle 1 Day 1 pre-dose (any time), between 0.5-1 hr post-dose, and between 2-4 hr post-dose, and Day 15 pre-dose (within 15 minutes prior to dosing), between 0.5-1 hr post-dose, and between 2-4 hr post-dose.

Disease assessments, including analysis of blood and bone marrow aspirates, will be performed at the end of Cycle 1 and Cycle 3 and every 2 cycles thereafter. Disease assessments may be performed at other time points at the discretion of the investigator.

Subjects who demonstrate objective response (OR) or stable disease (SD) will be allowed to continue therapy with FF-10501-01 until progression of disease, observation of unacceptable adverse events, intercurrent illness or changes in the subject's condition that prevents further study participation.

Blood for hematology, platelet and serum chemistry determinations will be collected within 28 days of Cycle 1 Day 1, on Days 1, 8, 15, and 22 of Cycle 1, on Day 1 of each subsequent cycle, and at the End of Study Visit. Urine will be collected for urinalysis within 28 days of Cycle 1, on Day 1 of each subsequent cycle and at the End of Study Visit.

Safety will be assessed through the monitoring of adverse events (AEs), clinical laboratory parameters (hematology, serum chemistry), vital sign measurements, electrocardiograms (ECGs) and physical examinations. Adverse events will be classified according to the Medical Dictionary for Regulatory Affairs (MedDRA) and graded according to the National Cancer Institute Common Terminology Criteria for Adverse Events (NCI CTCAE) version 4.03.

Efficacy assessment for AML will be performed using a modification of the recommendations of the International Working Group for Diagnosis, Standardization of Response Criteria, Treatment Outcomes, and Reporting Standards for Therapeutic Trials in Acute Myeloid Leukemia. Efficacy assessments for subjects with MDS or CMML will be performed using a modification of the International Working Group Response Criteria in Myelodysplasia. Efficacy assessments for any subject may be performed at other time points at the discretion of the investigator.

Pharmacokinetic determinations will be performed.

XMP will be determined in peripheral blood as a pharmacodynamics endpoint.

3.2. Number of Subjects and Centers

Phase 1: Up to 48 subjects are planned for the dose-escalation phase. Phase 2a: A total of 20 subjects with MDS/CMML treated at the RP2D are planned, including MDS/CMML subjects treated at the RP2D in Phase 1. Therefore, up to 68 subjects are planned.

The study will be conducted at up to seven sites.

3.3. Duration of Study

The accrual phase for the Phase 1 dose-escalation phase is expected to be 12 – 18 months. The expected accrual phase for the Phase 2a expansion phase is expected to be 6 – 12 months, with the last subject followed for up to 6 months, for a total study duration of 30 – 36 months. The anticipated accrual rate for the Phase 2a portion is 4 – 5 subjects per month.

3.4. Criteria for Termination of the Study

If the sponsor, investigator, study monitor, or officials from the Food and Drug Administration (FDA) discover conditions arising during the study that indicate that the study should be halted or that the study site should be terminated, this action may be taken after appropriate consultation between the sponsor and investigator.

Conditions that may warrant termination include, but are not limited to, the following:

- The discovery of an unexpected, serious, or unacceptable risk to subjects enrolled in the study
- A decision on the part of the sponsor to suspend or discontinue testing, evaluation, or development of the product
- Failure of an investigator to enroll subjects into the study at an acceptable rate

- Failure of an investigator to comply with pertinent FDA regulations
- Submission of knowingly false information from the study site to the sponsor, study monitor, or the FDA
- Insufficient adherence to protocol requirements

Study termination and follow-up would be performed in compliance with the conditions set forth in 21 CFR 312.50 and 21 CFR 312.56.

4. STUDY POPULATION

4.1. Inclusion Criteria

Subjects must meet all of the following criteria to participate in the study:

- Males and females \geq 18 years of age
- Subjects with confirmed hematologic malignancies:
 - Phase 1:
 - High-risk MDS/CMML (defined as \geq 10% peripheral blood or marrow blasts and/or International Prognostic Scoring System [IPSS]³⁴ score \geq 1.5) and relapsed or refractory to prior therapy
 - AML relapsed or refractory to prior therapy, or \geq 60 years of age and not a candidate for other therapies
 - Phase 2a:
 - MDS/CMML, relapsed from, or refractory to prior HMA therapy; the latter defined as failure to achieve clinical remission (CR), partial remission (PR) or hematologic improvement (HI) after previous HMA therapy (\geq 4 cycles of azacitidine or decitabine), or progression during, or toxicity to, previous HMA therapy precluding further HMA treatment, and
 - Bone marrow blast count \geq 10% or peripheral blast count \geq 5%, or IPSS-R³⁵ score \geq 3.5
 - At least 3 weeks beyond the last chemotherapy, targeted anticancer agent, major surgery or experiment treatment and recovered from all acute toxicities (\leq Grade 1). *Hydroxyurea used to control peripheral blast counts is permitted up to Day 7 of treatment on study.*
 - Adequate performance status: Eastern Cooperative Oncology Group (ECOG) \leq 2
 - Adequate renal and hepatic function:
 - Creatinine \leq 2.0 mg/dL, or calculated creatinine clearance \geq 45 mL/minute per the Cockcroft-Gault formula
 - Total bilirubin \leq 2 times the upper limit of normal (ULN)
 - ALT and AST \leq 2 times ULN

- Negative serum pregnancy test within 14 days prior to first dose of study therapy for women of child-bearing potential (WCBP), defined as a sexually mature woman who has not undergone a hysterectomy or who has not been naturally post-menopausal for at least 24 consecutive months (i.e., who has had menses any time in the preceding 24 consecutive months). Sexually active WCBP and male subjects must agree to use adequate methods to avoid pregnancy (oral, injectable, or implantable hormonal contraceptive; tubal ligation; intra-uterine device; barrier contraceptive with spermicide; or vasectomized partner) throughout the study and for 28 days after the completion of the study treatment.
- Ability to provide written informed consent

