5.6.2. Prohibited Therapy

Concurrent anti-tumor therapy of any kind or any other investigational agent is prohibited. Concomitant medication(s) that may cause QTc prolongation or induce Torsades de Pointes are prohibited, with the exception of anti-microbials that are used as standard of care to prevent or treat infections and other such drugs that are considered by the Investigator to be essential for the care of the patient. See **Appendix C** for a list of drugs that may cause QTc prolongation or induce Torsades de Pointes.

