7.2.3.2. Secondary Efficacy Endpoints

The proportion of subjects with MDS who have hematologic improvement in peripheral blood or bone marrow blast count at any time after initiation of treatment with FF-10501-

01. Hematologic improvement in blast count is defined as $\geq 50\%$ reduction in peripheral blood or bone marrow blast count when compared with the baseline value.

Progression-Free Survival: length of time from the date of first administration of study drug to the first objective evidence of disease progression or death, whichever is earlier.

Overall Survival: length of time from the date of first administration of study drug to the date of death from any cause

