8.3.2.2. Secondary Efficacy Endpoints

The proportion of MDS subjects with hematologic improvement in the peripheral blood or bone marrow as defined as $\geq 50\%$ reduction in blast count when compared with the baseline value. The 90% confidence interval will be estimated and provided.

Progression-free survival and overall survival curves will be estimated at the MTD by disease cohort using Kaplan-Meier product limit estimates. Median and 90% confidence interval of time-to-event will be estimated. Progression-free survival will be calculated from the date of first dose of study drug to the date of first objective evidence of disease progression or death, whichever is earlier. Overall survival will be calculated from the date of first dose of study drug to the date of death due to any cause. Subjects who did not experience progression or death will be censored at the last follow-up time point.

8.3.3. *Pharmacokinetic Endpoint Analysis*

Mean plasma concentrations of FF-10501 and plasma M1 will be determined at each time point for evaluation of dose-linearity. Because a limited number of plasma concentrations will be determined, full determination of routine pharmacokinetic parameters may not be possible. In addition to mean plasma concentrations, as the data allow, additional pharmacokinetic analyses will be provided (trough levels, $t_{1/2}$, T_{max} , C_{max} , AUC, etc.)

8.3.4. *Pharmacodynamic Endpoint Analysis*

Change from baseline in XMP levels will be measured in blood samples collected from each subject during the study. Correlations between XMP and PK levels of FF-10501 will be made. Pharmacodynamic parameters will be summarized using descriptive statistics

including the number of subjects, mean, standard deviation, minimum, median, maximum, range, and coefficient of variation.

8.3.5. *Other Summaries*

Demographics and concomitant medications, including antibiotic usage, will be summarized using descriptive statistics. Medical history findings and protocol deviations will be listed but not summarized.

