2.3.1.2. Baseline Values

The screening assessments are performed within 28 days of Cycle 1, Day 1, before the first dose of study medication. Unless otherwise mentioned, baseline will be the last observation before patients receive initially assigned dose. Generally, this will be Cycle 1 Day 1 pre-dose measurements. If a pre-dose assessment is not performed on Cycle 1 Day 1, the immediate previous non-missing value, including screening, will be treated as baseline. If there are multiple baseline assessments, the most recent one will be flagged as the baseline value and will be used for statistical analysis (evaluations may occur on the same day as Study Day 1, prior to dosing).

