3.3.2. Secondary Endpoints

The proportion of subjects with MDS who have hematologic improvement in peripheral blood or bone marrow blast count at any time after initiation of treatment with FF-10501-01. Hematologic improvement in blast count is defined as $\geq 50\%$ reduction in peripheral blood or bone marrow blast count when compared with the baseline value.

Progression-Free Survival: length of time from the date of first administration of study drug to the first objective evidence of disease progression or death, whichever is earlier.

Overall Survival: length of time from the date of first administration of study drug to the date of death from any cause.

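### In MDS subjects who take hydroxyurea, an early fall in peripheral blasts can be counted as improvement on FF-10501-01, because no rule links the blast endpoint to hydroxyurea dates

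*Protocol*

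**What the plan says.** Protocol 4.1 requires three weeks since the last chemotherapy, but for one drug it adds: "Hydroxyurea used to control peripheral blast counts is permitted up to Day 7 of treatment on study". The allowance is not limited by disease or phase, and the section sets no limit on starting or increasing the drug near Day 1.

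The secondary endpoint in protocol 7.2.3.2 is the proportion of "subjects with MDS who have hematologic improvement in peripheral blood or bone marrow blast count at any time after initiation of treatment", where improvement is at least a 50% "reduction in peripheral blood or bone marrow blast count when compared with the baseline value". SAP 3.3.2 repeats the definition. Protocol 8.3.2.2 adds only the interval: "The 90% confidence interval will be estimated and provided". None of these sections asks for confirmation, duration or a washout.

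Under SAP 2.3.1.2, "baseline will be the last observation before patients receive initially assigned dose", with no provision for a subject already on hydroxyurea. Hematology, which includes blasts percent (protocol Table 7), is drawn on Days 1, 8, 15 and 22 of Cycle 1 (Appendix D).

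Protocol 5.6.2 states that "Concurrent anti-tumor therapy of any kind or any other investigational agent is prohibited" and does not mention hydroxyurea.

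**The concern.** By the protocol's own description, hydroxyurea is given to move the variable that the endpoint measures. It may overlap the first week of study drug, and the endpoint is open from first dose. There is no control arm to separate the two drugs, and SAP 2.4.2 plans no hypothesis test, so the descriptive proportion and its 90% interval are the whole result. If some counted responders owe their status to hydroxyurea, the reported proportion overstates activity. If some baselines were already suppressed by it, the proportion may understate activity.

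**Working it through.** The plan gives no expected rate or bias for this endpoint, so there is no figure to reproduce. The check is of timing, of other rules that might prevent the overlap, and of what each error is worth.

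**Timing of the overlap**
- Last permitted hydroxyurea day: Day 7 (protocol 4.1).
- Day 8 visit: 8 - 1 = Day 7 to 8 + 1 = Day 9 (protocol 6.2.2), which is 0 to 2 days after the last permitted day. If the limit is read as excluding Day 7 itself, each gap grows by one day.
- First scheduled marrow after baseline: 28 - 3 = Day 25 to 28 + 3 = Day 31 (protocol 6.2.5), which is 18 to 24 days after Day 7.

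One Day 8 reading at half the baseline value or less is therefore enough to count.

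**Other rules that might prevent it**
- SAP 3.3 uses the per-protocol set, which SAP 2.2.3 defines as a valid baseline and at least one later assessment. A subject whose only later reading is Day 8 qualifies.
- SAP 2.3.1.1 leaves unscheduled assessments out of by-visit tabulations, but Day 8 is scheduled.
- SAP 3.2.4 classifies and summarises concomitant medications but does not link them to this endpoint.

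**What each error is worth**

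The 20 Phase 2a subjects are MDS and CMML together, while the endpoint is for MDS only. The MDS denominator is not stated, so n = 20 is its Phase 2a maximum.
- n = 20: one misattributed responder adds 1/20 = 5.0 points. With exact (Clopper-Pearson) 90% intervals, an assumed method since the plan names none, 2/20 = 10.0% (1.8 to 28.3) and 4/20 = 20.0% (7.1 to 40.1).
- n = 8 (the MDS count to date in protocol 1.7.2, used only as an illustration): 1/8 = 12.5 points.

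**Illustrative upward bias**

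Let p be the true response rate, h the share on hydroxyurea, and q the chance that hydroxyurea alone produces a qualifying fall. All three are assumptions. The expected observed rate is p + (1 - p)hq, so the bias is (1 - p)hq.
- Low: p = 20%, h = 10%, q = 30%: 0.8 x 0.1 x 0.3 = 2.4 points.
- High: p = 0, h = 30%, q = 70%: 1 x 0.3 x 0.7 = 21.0 points.

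This range leaves out the opposite bias from a suppressed baseline, so it is not an estimate of net bias.

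**What a date filter would admit after a Day 7 stop**
- 7-day interval: readings through Day 14 are excluded. The Day 15 draw (Days 14 to 16) counts if taken on Day 15 or later.
- 14-day interval: readings through Day 21 are excluded. The Day 22 draw (Days 21 to 23) counts only if taken on Day 22 or later; otherwise the next scheduled hematology is Cycle 2 Day 1.
- 21-day interval: readings through Day 28 are excluded. Cycle 2 Day 1 (nominally Day 29, +/- 3 days) counts if taken on Day 29 or later.

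**The case against.** The strongest reply is that the exposure is narrow. This is one route of one secondary endpoint in an uncontrolled study whose primary objective is safety. Only hydroxyurea users whose sole qualifying reading is an early peripheral one are affected. Objective response in MDS and CMML depends on marrow criteria, with marrow first scheduled well after Day 7. All of this stands, and it limits the weight of the point.

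Three stronger readings are tempting, and the documents do not support them.
- A reader might infer that the whole proportion cannot be attributed to FF-10501-01. Non-users are unaffected, and the marrow route is little affected.
- A reader might infer a definite inflation. The documents give no hydroxyurea use, no effect size and no MDS denominator. They also do not say whether the blast count in the endpoint is the blasts percent in Table 7 or an absolute count, which bears on how far hydroxyurea would move it. For established users the pre-dose baseline may already carry the effect, so even the direction is not fixed.
- A reader might infer that 4.1 and 5.6.2 flatly contradict each other. Section 4.1 can be read as a specific exception to a general ban. Neither section says so, and that is all that can be claimed.

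It can also be said that a repeat reading would settle the matter. A repeat during hydroxyurea exposure would not. A confirming reading well after the last dose largely would, and the fix allows for it.

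**Conclusion.** The concern holds in limited form. Followed as written, the plan can credit a hydroxyurea effect to FF-10501-01 through the peripheral-blood route in MDS subjects who took hydroxyurea, and no rule in either document prevents it. A baseline lowered by hydroxyurea can bias the result the other way. That the overlap is possible follows from the text and the visit windows alone. Its size is unknown: 5 points per misattributed responder if n = 20, more with fewer MDS subjects. The 2.4 to 21.0 point range rests wholly on assumed inputs. This is worth correcting in the analysis plan before the data are summarised, but it does not threaten the safety objective or, to any material degree, the primary response endpoint.

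**What to change.** In SAP 3.3.2:

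1. Using actual dates, do not count a peripheral blast reading taken on hydroxyurea, or within a fixed interval after its last recorded dose, unless a later reading outside that interval also meets the threshold. Fourteen days is a workable main interval, with a shorter and a longer one (for example 7 and 21 days) as sensitivity analyses. These are analytic assumptions; the documents give no carry-over time.
2. Report the proportion separately for MDS subjects with and without hydroxyurea between Day -28 and Day 7. This exposes the suppressed-baseline bias, which the date filter cannot remove.
3. State whether the peripheral measure is blasts percent or an absolute count.

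Protocol 4.1 and 5.6.2 must be reconciled on hydroxyurea; no clinical rule is proposed here.

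Cost: SAP wording, a date filter and one extra split in the hematologic improvement table. No new data are needed, since protocol 5.6.1 already records medications from four weeks before and throughout the study. Reconciling the protocol sections, or repeating the rule in 7.2.3.2, would take a protocol amendment with IRB approval (9.4). The downsides are that a genuine but brief early fall in a hydroxyurea user is not counted, users have a shorter window for a peripheral response than non-users, and the subgroups will be small.
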